1.5. Contraindications, Warnings, Precautions, and Adverse Reactions

1.5.1. Contraindications

Epinephrine Inhalation Aerosol is contraindicated in patients who are taking a prescription drug that contains phenylephrine, pseudoephedrine, ephedrine, or caffeine (for allergy, cough-cold, or pain), monoamine oxidase inhibitor (MAOI) (in certain drugs for depression, psychiatric or emotional conditions, or Parkinson's disease), or for 2 weeks after stopping the MAOI drug.

Albuterol Sulfate HFA is contraindicated in patients with a history of hypersensitivity to albuterol and any other Albuterol Sulfate HFA components.

1.5.2. Warnings and Precautions

Primatene Mist should be taken with precaution under certain conditions:

- ever been hospitalized for asthma
- heart disease
- high blood pressure
- diabetes
- trouble urinating due to an enlarged prostate gland
- thyroid disease
- seizures
- narrow angle glaucoma

Epinephrine injection should be used with precaution:

- more than two sequential doses of epinephrine should only be administered under direct medical supervision.
- Epinephrine injection should **only** be injected into the anterolateral aspect of the thigh
- rare cases of serious infections at the injection site may occur
- may trigger allergic reactions associated with sulfite in certain susceptible individuals
- patients with heart disease, hyperthyroidism, diabetes, Parkinson's disease (may notice a temporary worsening of symptoms), elderly individuals, and pregnant women should be carefully instructed in regard to the circumstances under which epinephrine should be used.

PROAIR should be taken with precaution and discontinue use under the following circumstances:

- paradoxical bronchospasm may occur
- deterioration of asthma
- not to substitute for use of anti-inflammatory agents
- cardiovascular effects may occur
- exceeding recommended dose may be fatal
- immediate hypersensitivity reactions may occur
- hypokalemia and changes in blood glucose may occur.

1.5.3. Adverse Reactions

The clinically observed adverse events are mainly related to its systemic adrenergic actions exerted by the small fraction of epinephrine that enters into the systemic blood circulation and interacts with the α - and β -adrenoceptors on the endothelia cells. The common and expected adverse event include: Increased blood pressure and heart rate (which could lead to more serious problems such as heart attack and/or stroke), nervousness, sleeplessness, rapid heartbeat, tremor, seizure, etc. Rarely, bronchial irritation and edema may occur. In some patients, severe prolonged asthma attacks may be precipitated. Rebound bronchospasm may occur when the effects of epinephrine end.

Adverse reactions to epinephrine include anxiety, apprehensiveness, restlessness, tremor, weakness, dizziness, sweating, palpitations, pallor, nausea and vomiting, headache, and/or respiratory difficulties.

Most common adverse reactions associated with the use of PROAIR are headache, tachycardia, pain, dizziness, pharyngitis, and rhinitis.

Use of Albuterol Sulfate HFA may be associated with the following:

- paradoxical bronchospasm;
- cardiovascular effects;
- immediate hypersensitivity reactions; and
- hypokalemia
- Hyperglycemia.

1.6. Drugs with Strong Impact on PK or PD

Drugs with impact on PK: Short-acting sympathomimetic aerosol bronchodilators and adrenergic drugs.

Drug with Impact on PD and safety: (i) Non-selective α -blockers; (ii) Beta-blockers; (iii) Diuretics, or non-potassium sparing diuretics may potentiate hypokalemia or ECG changes; (iv) Digoxin; (v) Monoamine oxidase (MAO) inhibitors; (vi) Sympathomimetics; (vii) Thyroid hormones; and (viii) tricyclic antidepressants.

A list of drugs, which have strong impact on PK or PD profile for epinephrine and Albuterol, is provided in [Appendix III](#).

2. OBJECTIVES

2.1. *Objective*

To assess the drug exposure profile in systemic circulation of Primatene® Mist by inhalation, versus Epinephrine by IM, and ProAir® HFA by inhalation in healthy adults

2.2. *Primary Endpoints*

- AUC_{0-6h} , defined as area under the curve (AUC) concentration curve over time, from time 0 to 6 hours post-dose for Epinephrine;
- AUC_{0-24h} , defined AUC of plasma Albuterol concentration curve over time 0 to 24 hours post-dose;
- $AUC_{0-\infty}$, defined as AUC in the plot of plasma Albuterol, or Epinephrine versus time from time 0 to infinity; and
- C_{max} , defined as the maximum plasma concentration of Albuterol, or Epinephrine.

2.3. *Secondary Endpoint*

- t_{max} of Albuterol, or Epinephrine, defined as the time, at which the C_{max} is observed; and
- $T_{1/2}$, terminal elimination half-life of each analyte.

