At each sampling point, the first 1 mL of blood will be discarded for waste (utilizing a disposable tube), and blood samples (~5 mL) will be collected in ice-chilled potassium-EDTA sample tubes, mixed well immediately following collection, kept on ice or refrigerated and centrifuged within 20 minutes of collection. All blood samples will be centrifuged at 4°C, 2,000-3,000 g for 20 minutes for plasma isolation. Isolated plasma will be distributed into two (2) aliquots, approximately 1.5 mL in the first aliquot and the remainder in the second aliquot. The plasma sample vials will be frozen immediately on dry ice and then stored (within 60 minutes following plasma separation) in a freezer at -20°C or lower until analysis.

3) PK Sample ID

The sample ID for PK blood samples (before centrifugation) is defined as:

EIPK-nn-V-XX

where **EIPK-nn** is the subject ID, **V** is the dosing visit code, **V=1 to 3**, and **XX** is the two-digit time-point sequential number of the sample: 01, 02, 03, ... 26 as listed in **Table B**.

The sample ID for PK plasma samples (after centrifugation) is defined as “**EIPK-nn-V-XX-k**” and **k** is the aliquot number (A or B). The PK plasma sample ID labels, with the size of 1/2”×1¾” (Avery label 5667), should be printed in blue font as demonstrated below:

EIPK-nn-V-XX-k

4) Sample Transportation and Analysis

The chain of custody, temperature control, and related documents for sample transportation must

be recorded. During transportation of PK samples from the site to Amphastar, the temperature should be below -20°C. PK samples will be analyzed with an established LC/MS/MS method for detection of Epinephrine and Albuterol.

V. Study Evaluations

1) Primary Endpoints

- AUC_{0-6h} , defined as area under the curve (AUC) concentration curve over time, from time 0 to 6 hours post-dose for epinephrine;
- AUC_{0-24h} , defined AUC of plasma Albuterol concentration curve over time 0 to 24 hours post-dose;
- $AUC_{0-\infty}$, defined as AUC in the plot of plasma Albuterol, or Epinephrine versus time from time 0 to infinity; and
- C_{max} , defined as the maximum plasma concentration of Albuterol, or Epinephrine.

2) Secondary Endpoints

- t_{max} of Albuterol, or Epinephrine, defined as the time, at which the C_{max} is observed; and
- $T_{1/2}$, terminal elimination half-life of each analyte.

3) Additional Evaluations

- Relative Bioavailability of Treatment-A (E004 inhalation) over Treatment-B (IM epinephrine injection);

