6.1.1. Per-Protocol Population (PPP)

The “Per Protocol” population is defined as all subjects who have received all study medications during the study and are evaluable for all treatments. The primary analyses will be performed based on “Per Protocol” population (PPP).

An evaluable subject for primary analyses of this study must meet all of the following ten (10) items for both treatments:

- (1) Correct dose and administration;
- (2) Nineteen (19) or more of 25 post-dose PK data points (>75%) are available;
- (3) There are no more than four (4) consecutive missing PK data points;
- (4) The baseline PK data point is available;
- (5) For Treatment-A, at least four (4) of the five (5) PK data points at 1, 2, 3, 5, and 7 minutes post-dose are available;
- (6) For Treatment-B, at least four (4) of the five (5) PK data points at 9, 12, 15, 18, and 21 minutes post-dose are available;
- (7) For Treatment-C, at least four (4) of the five (5) PK data points at 25, 30, 40, 50, and 60 minutes post-dose are available;
- (8) For Treatment-A, at least three (3) of the PK data points at 25, 30, 40, and 50 minutes post-dose are available.
- (9) For Treatment-B, at least three (3) of the PK data points at 80, 90, 120 minutes and 4 hours post-dose are available; and
- (10) For Treatment-C, at least three (3) of the PK data points at 6, 8, 12 and 18 hours post-dose are available.

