6.2. PK Results Evaluations

6.2.1 Calculation of Primary Endpoints

- C_{max} will be obtained directly by observing the plot of PK curve;
- AUC_{0-6h} and AUC_{0-24h} will be calculated with trapezoid method;
- $AUC_{0-\infty}$ will be calculated with extrapolation method.

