2.1 PRIMARY ENDPOINTS

- AUC_{0-t} , defined as area under the curve (AUC) concentration curve over time, from time 0 to the time when Epinephrine reduced to the baseline post-dose for exogenous Epinephrine;
- AUC_{0-24h} , defined AUC of plasma Albuterol concentration curve over time 0 to 24 hours post-dose;
- $AUC_{0-\infty}$, defined as AUC in the plot of plasma Albuterol, or exogenous Epinephrine versus time from time 0 to infinity; and
- C_{max} , defined as the maximum plasma concentration of Albuterol, or Epinephrine.

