4. CALCULATION OF RELATED STATISTICAL QUANTITIES

4.1 PK/PD PARAMETERS

4.1.1 Primary Endpoints

(1) C_{max} , in units of pg/mL, is defined as the maximum of experimental data points of epinephrine or albuterol concentration for a given subject and given treatment:

[figure not shown]
$$C_{max} = \max (C_1 \cdots C_i \cdots C_n) \quad i = 1, 2, 3 \cdots n \quad (1)$$

where C_i is the observed plasma concentration of albuterol or epinephrine at the time t_i ; which is the sampling point time;
 t_1 is the baseline, and n is the number of available PK measurements.

(2) $AUC_{0-t_m}^{Tot}$ for Total API,

As is demonstrated in the left plot of **Figure 1**, the AUC is for total API, including both exogenous and endogenous, if the endogenous active ingredient exists, such as epinephrine for Treatments A and B.

Figure 1 AUC for Total Active Ingredient (left) and Drug Exposure (right)

$AUC_{0-t_m}^{Tot}$ is reported in units of pg/mL*hr, can be calculated per the trapezoidal rule as given the Eq. (2):

$$AUC_{0-t_m}^{Tot} = \sum_{i=1}^{m-1} \frac{C_i + C_{i+1}}{2} (t_{i+1} - t_i) \quad (2)$$

where

- t_m is the time of the first PK point for the subject and the treatment, after C_{max} , that is reduced to the same day baseline (C_0), if C_0 is detectable, such as for epinephrine, (see **Fig. 1**, left plot); and
- $t_m > t_{max}$, and is the smallest time point that meets

$$C(t_m) \leq C_0 + \frac{1}{2} QL \quad (3)$$

- $t_m = 24$ hrs for albuterol, or m is the number of available PK measurements until t_m .

(3) The AUC for Drug Exposure $AUC_{0-t_m}^{DE}$

The AUC for the drug exposure, as is demonstrated in the right plot of **Figure 1**, is the AUC for exogenous API, if the endogenous active ingredient exist such as epinephrine for Treatments A and B.

$AUC_{0-t_m}^{DE}$ is reported in units of pg/mL*hr, and is calculated as follows:

$$AUC_{0-t_m}^{DE} = AUC_{0-t_m}^{Tot} - C_0 t_m \quad (4)$$

where $AUC_{0-t_m}^{Tot}$ and t_m is obtained based on Eqs. (2) and (3).

(4) **Drug Exposure $AUC_{0-\infty}$** (in units of pg/mL*min) is defined as below

$$\begin{cases} AUC_{0-\infty} = AUC_{0-t_m}^{DE} & \text{if } t_m < 24 \text{ hrs} \\ AUC_{0-\infty} = AUC_{0-t_m}^{DE} + AUC_{t_m-\infty}^{DE} & \text{if } t_m = 24 \text{ hrs} \end{cases} \quad (5)$$

$AUC_{t_m-\infty}$ can be obtained per the extrapolation method as given in the Eqs. (6) –(7) below, based on the time is long enough so that

$$C(t) \approx Be^{-k_e t}, \quad (6)$$

thus

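### The primary epinephrine AUC is an uncorrected fixed 0–6 h area in the protocol but a baseline-corrected area to a subject-specific time in the SAP, which assigns no end time if baseline is never regained

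*Protocol*

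**What the plan says.** **Protocol.** Section 2.2 lists among the primary endpoints an AUC "from time 0 to 6 hours post-dose for Epinephrine", and synopsis V does the same ("from time 0 to 6 hours post-dose for epinephrine"). Section 6.2.1 says AUC0-6h and AUC0-24h "will be calculated with trapezoid method" and that AUC0-∞ is extrapolated. Neither place mentions subtracting a baseline. The pre-dose sample enters the analysis section only as evaluability item 4 of section 6.1.1 ("The baseline PK data point is available").

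**SAP.** AUC0-6h does not appear. Section 2.1 replaces it with an AUC "from time 0 to the time when Epinephrine reduced to the baseline post-dose for exogenous Epinephrine". In section 4.1.1, tm "is the time of the first PK point for the subject and the treatment, after" Cmax that has come back to that day's baseline. Formally it lies beyond tmax "and is the smallest time point that meets" Eq. (3), C(tm) ≤ C0 + QL/2. Eq. (4) subtracts C0·tm from the total area. Eq. (5) sets AUC0-∞ equal to that corrected area when tm < 24 h and adds an extrapolated tail when tm = 24 h. The value tm = 24 h is assigned to albuterol only. The SAP cites protocol version 1.1 but does not say that it changes that protocol's endpoint, or why.

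**RBA.** Protocol synopsis V lists "Relative Bioavailability of Treatment-A (E004 inhalation) over Treatment-B (IM epinephrine injection" as an additional evaluation. Both documents (protocol 6.2.4, SAP 5.3.2.3) define it with AUC0-∞. The SAP tabulates it per subject and reports the mean.

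**The concern.** The objective is systemic exposure of inhaled against IM epinephrine, and the SAP background expects the inhaled exposure to be much the lower. Two consequences follow from the text.

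1. Epinephrine is endogenous. A fixed-window AUC without subtraction adds the same area to both arms, and that area can be large beside a small inhaled exposure. The description of a primary endpoint then depends on which document is followed.
2. The SAP definition removes the endogenous area but is incomplete. C0 is one pre-dose sample. If it happens to be low, later samples may stay above C0 + QL/2 for many hours, or to the end, and the corrected area accumulates endogenous hormone over a long window. Through Eq. (5), AUC0-∞ and RBA inherit this.

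**Working it through.** Neither document reports a value for this AUC, so there is no figure to reproduce. The conflict is established by the text; the arithmetic only shows its possible size.

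**Step 1: endogenous area in the protocol AUC.** Protocol 1.4 gives a mean baseline of 0.23 nmol/L and equates 1.50 nmol/L with 275 pg/mL.
- Conversion: 275 / 1.50 = 183.3 pg/mL per nmol/L.
- Baseline: 0.23 × 183.3 ≈ 42.2 pg/mL.
- Over 6 h: 42.2 × 6 ≈ 253 pg·h/mL in each epinephrine arm.

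**Step 2: effect on the comparison.** Let B be the corrected IM area and r the corrected A/B ratio. The uncorrected ratio is (253 + rB)/(253 + B), which lies between r and 1 when r < 1. For r = 10% it is 7.5 times r at B = 100 pg·h/mL and 3.7 times r at B = 600. For r = 50% the factors are 1.7 and 1.3. These values of r and B are assumptions.

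**Step 3: one noise-free example on the protocol's sampling times.** Assume baseline 42 pg/mL. Above baseline, A peaks at 150 pg/mL at 2 min (half-life 5 min) and B at 300 pg/mL at 12 min (half-life 40 min).

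| Rule | A | B | A/B |
|---|---|---|---|
| Protocol, 0–6 h, uncorrected | 273 | 586 | 0.47 |
| SAP Eqs. (2)–(4), QL 5–20 | 20–21 | 327–334 | 0.06 |

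**Step 4: how tm behaves when the endogenous level varies.** SAP Eqs. (1)–(5) were applied to simulated profiles on the 26-point schedule. The endogenous level was flat on average (mean 42.2 pg/mL) with independent lognormal variation, CV 10–30%, and QL was 2–10 pg/mL. The rise to peak was linear, followed by exponential decline. Profiles that never met Eq. (3) were run to 24 h without extrapolation.
- Setting 1: A peak 38 pg/mL at 2 min, half-life 4 min; B peak 250 at 12 min, half-life 30 min.
- Setting 2: A peak 100 at 2 min, half-life 6 min; B peak 350 at 12 min, half-life 45 min.

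| | Setting 1 | Setting 2 |
|---|---|---|
| True RBA | 2.0% | 3.7% |
| SAP mean RBA | 2.3–18% | 4.0–11% |
| Median RBA | 1.7–2.0% | 3.5–3.7% |
| Mean RBA, window ended at min(tm, 6 h) | 2.1–7% | 3.9–6.5% |

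The mean is therefore between 4.0/3.7 ≈ 1.1 and 18/2.0 = 9 times the truth. Eq. (3) was never met in 0.2–6% of A profiles and 1.5–15% of B profiles across both settings.

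Setting 2 is close to what the roughly 5% bioavailability in protocol 1.4 would imply if IM absorption were complete, which is itself an assumption: 5% × 0.25/0.30 = 4.2%.

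**The case against.** **Nothing inferential depends on this.** That stands. Neither document has a hypothesis test, margin, alpha or power figure for epinephrine. Endpoints are listed, compared and averaged, and AUC0-6h could be computed later from the same samples.

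**The contrast in steps 2 and 3 is not a planned ratio.** Also correct. A reader might infer that the trial would report an A/B ratio near 50% in place of a few per cent. The only planned ratio is RBA, and it uses AUC0-∞ in both documents. The distortion concerns the side-by-side comparison of primary AUCs, and only on a literal reading. The protocol hints at a correction, since it requires a baseline sample and an epinephrine AUC0-∞ is finite only with one. Reading a correction in does not remove the conflict, because the windows still differ: in setting 2 the ratio of arm means is about 3.8% over fixed 0–6 h and roughly 4–9% over 0–tm.

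**The SAP does cover profiles that do not return.** Partly. Eq. (5) has a 24 h branch, Eq. (7) names epinephrine, and Eq. (9) gives a baseline-adjusted slope for Treatments A and B. It would be wrong to say that the SAP is silent. But these equations only imply an extrapolation for AUC0-∞. None sets tm for AUC0-tm.

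**The assumed variability is generous.** Protocol 1.4 reports 0.23 ± 0.02 nmol/L in six volunteers. That is a CV of about 9% (0.02/0.23) if the spread is an SD, or about 21% (0.02 × √6/0.23) if it is a standard error; the text does not say which. Over CV 9–21%, mean RBA in setting 2 was 3.9–9.0%, so some inflation remains. The same section reports return to baseline 20 min after 4.8 mg inhaled. That supports a short true exposure, but it does not prevent a late tm caused by one low pre-dose value.

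**Biased baselines.** One might argue that catheter placement raises the pre-dose value, or that movement and meals raise later values, and so predict a direction of error. The documents give no figure for either, so no such claim is made.

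**Conclusion.** The definition conflict is certain from the text: interval and quantity both differ, and the SAP does not acknowledge the change. The missing end-of-window rule for epinephrine is also textual, subject to the fallback implied for AUC0-∞.

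The sizes are illustrative. The 253 pg·h/mL per arm rests on the protocol's cited baseline and a literal reading of its AUC. The 1.1- to 9-fold inflation of mean RBA rests on assumed profiles, QL and endogenous variability with a flat mean level. It arises where inhaled exposure is small, and the median is little affected.

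This should be fixed, but the documents do not support the stronger inference that a trial conclusion turns on it. High confidence belongs to the conflict in definition, not to any particular magnitude.

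**What to change.** 1. Use one definition in both documents: the baseline-corrected AUC of SAP Eq. (4), replacing the uncorrected AUC0-6h in protocol synopsis V, 2.2 and 6.2.1.
2. State where the window ends for Treatments A and B when Eq. (3) is met late or never. Ending it at min(tm, 6 h), with the protocol's own 6 h limit, is one workable rule.
3. Apply the same rule where Eq. (5) feeds AUC0-∞ and RBA, and say so. Under that rule the epinephrine AUC0-∞ is the same number as the windowed AUC.
4. Report the median RBA beside the mean.
5. Optionally, report a baseline-corrected fixed 0–6 h AUC as a sensitivity analysis.

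The cost is wording; no new data are needed. A 6 h limit cuts a little of the IM area: at an assumed 45 min half-life and a 12 min peak, (1/2)^(348/45) ≈ 0.5% of the post-peak area. It narrows the inflation (step 4) but does not remove the dependence on a single pre-dose sample.

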3. INVESTIGATORS AND STUDY SITES

3.1. Principal Investigator(s)

Principal Investigators (PI) responsible for the conduct of this study will be board certified physicians who are familiar with the study medications and trained to handle any untoward events related to medications.

The PI is responsible for the global aspects of the research study. For safety monitoring, a study physician or healthcare professional, who is certified for Advanced Cardiac Life Support, will be available at the study site at the time of study drug administration and during the entire time of PK blood sampling period. The Institutional Review Board (IRB) acknowledges one PI per study site. Qualifications for the PI and Co-Investigator(s) are listed on the Form FDA 1572.

3.2. Investigational Site(s)

The detailed information about the study site can be found on Form FDA 1572, including: Name, address, and statement of qualifications of each Principal Investigator; name of each sub-Investigator working under the supervision of the Investigator; name and address of the research facilities to be used; name and address of each reviewing IRB per US 21 CFR 312.23 section 6(iii)(b).

3.3. Laboratory

Samples of blood for evaluation of hematology and chemistry (metabolic panels) will be analyzed by the clinical laboratory with certification from a recognized accreditation agency (e.g., College of American Pathology or Clinical Laboratory Improvement Amendments certification). Refer to [Appendix IV](#) for a list of parameters analyzed, and the laboratory manual for details regarding specimen sample collection, processing, and shipment procedures. PK samples will be processed and analyzed by R&D Department, Amphastar Pharmaceuticals, Inc.

4. MATERIALS AND METHODS

4.1. *Study Design*

This is a randomized, safety evaluator-blind, three-treatment, crossover, fasting study in healthy adults (18 - 50 years of age).

4.2. *Study Subjects*

4.2.1. Sample Size

A total of at least 24 evaluable healthy adult volunteers will take part in this crossover study.

4.2.2. Subject Enrollment

A sufficient number of candidates will be screened to ensure 24 evaluable subjects will be enrolled into the study based upon the satisfaction of the inclusion and exclusion criteria. Informed consent will be obtained prior to performing any screening procedures.

4.2.3. Inclusion Criteria:

Candidates will be qualified only if they meet **all** of the following criteria:

- (1) Agree to participate; understand and sign informed consent;
- (2) Male and female adults, aged 18 to 50 years, inclusive at Screening;
- (3) Generally healthy and medically stable, with no clinically significant abnormalities based on physical examination and laboratory tests as determined by the Investigators;
- (4) Have good venous access;
- (5) Have normal resting blood pressure and normal heart rate (HR) without history of syncope; a subject with out of range blood pressure may be enrolled in the study at the discretion of the Principal Investigator;
- (6) Have a body mass index (BMI) of 18.0 – 30.0 kg/m²;
- (7) Female candidates must be >1 year post-menopausal or practicing a clinically acceptable form of birth control and confirmed by negative urine or serum pregnancy test at Screening;
- (8) Negative HIV-Ab, HBs-Ag and HCV-Ab;
- (9) Negative alcohol test (urine or breathalyzer);
- (10) Negative drug screening results;
- (11) Currently non-smoker; have not used any tobacco products for at least three (3) months prior to Screening; and

(12) Demonstrate proficiency in the use of MDI and a consistent inhalation time >2.0 seconds after training, for at least three (3) times, with a maximum of 5 attempts.

